9.5 Early Study Termination

This study can be terminated at any time for any reason by the PI-sponsor. If this occurs, all subjects on study should be notified as soon as possible. Additional procedures and/or follow up should occur in accordance with Section 12.6.2.

10 STUDY DRUG

10.1 Names, Classification, and Mechanism of Action

PVSRIPO is a modified version of the serotype 1 live-attenuated (Sabin) PV vaccine (PV1) and its immunogenic properties and potential for long-term sequelae are expected to be similar. PV1S has been safely administered to >10 billion individuals worldwide without untoward long-term sequelae. The only known effect of PV1S administration to human subjects is neutralizing immunity to PV.

[figure not shown]

Figure 3. Genetic structure of PVSRIPO.

PVSRIPO is PV1S containing a heterologous IRES of HRV2 (Figure 3). The IRES is a *cis*-acting, non-coding genetic element within the 5' untranslated region (UTR) of all enteroviruses and is essential for translation of the viral genome. PVSRIPO is a non-enveloped, positive-sense ssRNA virus with a genome of ~7300 nucleotides (nt) in length (Figure 3). PVSRIPO particles consist of a proteinaceous capsid composed of 60 copies of each of 4 capsid proteins (VP1-VP4) arranged in icosahedral geometry. Since the coding regions for the viral polyprotein (giving rise to all viral polypeptides) of PVSRIPO and PV1S are the same, the physical structure of the viral capsid and all non-structural viral polypeptides of PVSRIPO and PV1S are identical.

10.2 Packaging and Labeling

PVSRIPO is formulated in 50 mM sodium phosphate in 0.9% sodium chloride, pH 7.4 with 0.2% human serum albumin. It is provided in sterile, single use containers. PVSRIPO was manufactured at the Biopharmaceutical Development Program/SAIC-Frederick at NCI-Frederick. Prior to October 31, 2019, for tracking intratumoral/intracerebral distribution of the inoculum, the study agent suspension was supplemented with gadolinium-DTPA diamide (Magnevist®) at a final concentration of 1 mM and Magnevist® was stored at room temperature. Magnevist® is no longer being manufactured in the US so has been removed from the infusate along with the corresponding post-infusion MRI within 4h of infusion.

10.3 Supply, Receipt, and Storage

Refer to the study Investigational Product Handling Plan (IPHP) for details regarding supply, receipt and storage of study materials. The study agent and vehicle will be supplied directly to Investigational Chemotherapy Service (ICS) by the Sponsor (or designee). The study agent will be shipped via approved methods in the appropriate packaging on dry ice.

PVSRIP0 should be stored long-term in an ultra-low temperature freezer (e.g., a $\leq -80^{\circ}\text{C}$ freezer). Thawed vials should be kept at 4°C whenever possible. Thawed vials of PVSRIP0 are stable at 4°C for 48 hours. Once thawed, it is a clear colorless liquid with no evidence of particulates or foreign matter.

10.4 Dispensing and Preparation

Refer to the study IPHP for details of PVSRIP0 dispensing and preparation. In brief, preparation of PVSRIP0 will occur in a biosafety cabinet designated for viral vector agents. For thawing, vials containing PVSRIP0 should be removed from the -80°C freezer and kept at room temperature. PVSRIP0 contained in the clinically intended delivery apparatus is stable at room temperature for 18 hours, but should be used as soon as possible. The vials contain a clear, aqueous solution, which does not require reconstitution. **Do not thaw with heating devices (waterbath, heat-block) as a loss of potency may result. Do not expose vials to UV-light (in biosafety cabinets), as a loss of potency will result.** Thawed vials should not be re-frozen/thawed for later use, because potency may be lost. Thawed vials/study syringes containing PVSRIP0, which were kept for >48 hrs at 4°C prior to the infusion procedure, should be discarded, as a loss of potency may have occurred. Thawed vials/study syringes containing PVSRIP0, which were exposed for >12 hrs at room temperature prior to the infusion procedure, shall be discarded as a loss of potency may have occurred. For aliquot preparation, the agent will be thawed slowly on ice ($\sim 4^{\circ}\text{C}$) and kept at that temperature. The vials take approximately 30 minutes to thaw. The manufacturer will provide the study agent's potency (as tissue culture infectious doses) and will also supply the appropriate vehicle for aliquot preparation. Aliquot preparation will occur in the ICS. All handling of the study agent will occur in a biosafety cabinet or a similarly contained environment.

Any materials in contact with the study agent, e.g. syringes, vials, etc., will be disposed of as biological waste. The final desired aliquot of the study agent infuse will be prepared at the intended volume sufficient for priming the infusion tubing and for infusion. . The capped infusion syringe containing infuse (and primed infusion tubing if primed in pharmacy) will be transported to the study site in a 'ziplock' bag placed in a portable cooler or similarly contained transport device with a frozen ice block/ice pack, in order to maintain a temperature of approximately 4°C . No need to monitor the temperature during transport to the bedside.

10.5 Compliance and Accountability

Drug accountability records will be maintained for all clinical trial supplies. All empty and partially used clinical trial supplies will be destroyed in accordance with institutional guidelines. ICS will maintain detailed documentation of the receipt and/or destruction of the study agent. All materials coming in contact with the study agent, the syringe delivered from ICS, tubing, dressings or coverings used to protect the trepanation site, will be disposed of as biological waste in the treatment room.

10.6 Disposal and Destruction

All surgical materials used in the procedure and (potentially) coming in contact with the study agent will be disposable. These materials will be disposed of as biological waste using established procedures. Used sharps will be disposed in biohazard sharps container and incinerated for final disposal.

11 SUBJECT ELIGIBILITY

11.1 Inclusion Criteria

1. Patients must have a recurrent supratentorial WHO Grade III malignant glioma (anaplastic astrocytoma, anaplastic oligoastrocytoma, anaplastic oligodendrogloma, anaplastic pleomorphic xanthoastrocytoma, ependymoma) or WHO Grade IV malignant glioma, medulloblastoma, or atypical teratoid/rhabdoid tumor (ATRT) based on imaging studies with measurable disease (≥ 1 cm and ≤ 5.5 cm).

- a. The prior histopathology must be consistent with a World Health Organization (WHO) Grade III or IV malignant tumor confirmed by the study pathologist, [name], or his designee.
- b. The tip of the infusion catheter can be placed \geq 1cm from any ventricle.
- 2. There is no standard of care treatment for children with Grade III/IV gliomas; however, patients must have received some form of definitive treatment, i.e., standard therapy with known clinical benefit, for their initial diagnosis prior to their recurrence/progression. Definitive treatment includes maximal safe resection (if possible) and radiation therapy with or without chemotherapy. (*Please note that patients who are unable to receive radiation therapy due to genetic disorders that put them at significant risk for radiation-induced secondary malignancies (i.e., Gorlin's syndrome or NF1 mutation) are still eligible to participate.*)
- 3. All patients must be \geq 4 years of age and \leq 21 years of age at the time of entry into the study.
- 4. The patient must have a Lansky or Karnofsky Performance Score (KPS) of \geq 70% at the time of entry.
- 5. Laboratory Studies:
 - a. Platelet count \geq 125,000/ μ l prior to biopsy. Platelets \geq 100,000/ μ l prior to infusion;
 - b. Prothrombin and Activated Partial Thromboplastin Times \leq 1.2 x upper limit of normal (ULN) prior to biopsy;
 - c. Positive serum anti-poliovirus titer \geq 1:8 prior to biopsy;
 - d. Creatinine \leq 1.2 x ULN prior to biopsy;
 - e. Total bilirubin, AST, ALT, alkaline phosphatase \leq 2.5 x ULN prior to biopsy;
 - f. Neutrophil count \geq 1000 / μ l prior to biopsy;
 - g. Hemoglobin \geq 9 gm/dl prior to biopsy (can be transfused).
- 6. The patient must have received a boost immunization with trivalent inactivated IPOL™ (Sanofi-Pasteur) \geq 1 week prior to administration of the study agent.
- 7. At the time of biopsy, prior to administration of virus, the presence of recurrent tumor must be confirmed by histopathological analysis.
- 8. A signed informed consent form approved by the Duke University Institutional Review Board (IRB) will be required for patient enrollment into the study. Patients (if 18 years old) or their parent(s) or guardian(s) (if younger than 18 years old) must be able to read and understand the informed consent document and must sign the informed consent indicating that they are aware of the investigational nature of this study. Children who are \geq 12 years old and $<$ 18 years old should provide written assent to participate in the study. Children who are \leq 6 years old and $<$ 12 years should provide verbal assent to participate in the study.

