5 PROTOCOL SYNOPSIS AND RESEARCH SUMMARY

5.1 Purpose

The purpose of the study is to confirm the safety of the selected dose and potential toxicity of oncolytic poliovirus (PV) immunotherapy with PVSRIPO for pediatric patients with recurrent WHO grade III or IV malignant glioma, but evidence for efficacy will also be sought.

Primary Objective:

1. Confirm the safety of the selected dose of PVSRIPO when delivered intracerebrally by convection-enhanced delivery (CED) in children with recurrent WHO Grade III malignant glioma (anaplastic astrocytoma, anaplastic oligoastrocytoma, anaplastic oligodendrogloma, anaplastic pleomorphic xanthoastrocytoma, ependymoma) or WHO Grade IV malignant glioma (glioblastoma, gliosarcoma)

Secondary Objective:

1. Estimate Overall Survival (OS) in children with recurrent WHO grade III and IV malignant glioma treated with a single dose of PVSRIPO

Exploratory Objectives:

1. Describe changes visualized on imaging due to intratumoral inoculation of PVSRIPO
2. Describe changes in tumor volume visualized on imaging after intratumoral inoculation of PVSRIPO
3. Assess immunologic responses in peripheral blood and in serum
4. Identify genetic predictors of response or failure of response to treatment with PVSRIPO

Hypothesis:

Intracerebral injection of PVSRIPO will be feasible and safe in children with WHO grade III or IV malignant glioma.

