The Food and Drug Administration (FDA) recommended that the pediatric trial initially enroll patients 12 years of age and older and up to and including 18 years of age. We are including a number of WHO grade III and IV malignant brain tumor histologies and tumor locations in this trial. Specifically, eligible patients may include patients with recurrent WHO Grade III gliomas, such as anaplastic astrocytoma, anaplastic oligoastrocytoma, anaplastic oligodendrogloma, anaplastic pleomorphic xanthoastrocytoma, or ependymoma, as well as patients with WHO Grade IV gliomas, including glioblastoma or gliosarcoma. CD155 is avidly expressed in medulloblastoma, atypical teratoid rhabdoid tumor (ATRT), and embryonal tumors ²⁶, so these histologies will be included here as well.

Given that the incidence of embryonal tumors, ependymoma, and glioma peaks at ages lower than the initial eligible age for this clinical trial (≥ 12 years old), the study has experienced relative challenges to enrollment during its first two years. The incidence of the aforementioned tumor types is higher in younger children approximately 5 to 9 years of age and then continuously falls after 9 years old to a nadir in early adulthood ^{27,28}. In addition, the biology of brains in children aged 4 to 11 and the biology of the predominant types of brain tumors seen in this age range (i.e., glioma, ependymoma, and medulloblastoma) are similar to that of children who are 12 and over ¹. Tumors in children younger than 4 years old tend to have different genotypes and thus behave differently than tumors in children older than 4 years old ¹. There are currently active pediatric clinical trials in the US investigating the use of different oncolytic viruses, such as herpes simplex virus-1 (HSV-1) (NCT03911388 and NCT02451845) and a modified measles virus (NCT02962167), in a similar pediatric population. These trials also deliver the oncolytic virus via intratumoral administration and

include a population of children ranging in age from 3 to 18 years old in the case of aforementioned HSV-1 trial and children and adults ranging in age from 1 to 39 years old in the case of the modified measles virus.

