8 OBJECTIVES AND ENDPOINTS

Table 1. Objectives and Endpoints

	Objective	Endpoint	Analysis
Primary	Confirm the safety of the selected dose of PVSRIPO when delivered intracerebrally by convection-enhanced delivery (CED) in children with recurrent Grade III or IV MG	Percentage of patients that experience unacceptable toxicity during the 14-day period post-PVSRIPO treatment. Proportion of patients who require low-dose bevacizumab or steroid treatment due to an inflammatory reaction secondary to an immune response to PVSRIPO treatment will be calculated.	See Section 15.4
Secondary	Estimate Overall Survival (OS) in children with recurrent WHO Grade III and IV malignant glioma treated with a single dose of PVSRIPO	Proportion of patients alive 2 years after PVSRIPO treatment	See Section 15.5

Exploratory	Describe changes visualized on imaging due to intratumoral inoculation of PVSRIPO	Description of imaging changes	See Section 15.6
Other Exploratory	Describe changes in tumor volume visualized on imaging after intratumoral inoculation of PVSRIPO	Change from baseline in tumor volume based on imaging	See Section 15.7
Other Exploratory	Assess immunologic responses in peripheral blood and in serum	Change from baseline in immune function	See Section 15.7
Other Exploratory	Identify genetic predictors of response or failure of response to treatment with PVSRIPO	Identification of genetic markers as predictors of response	See Section 15.7

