9.4 Definition of Evaluable Subjects

Any patient who has undergone surgery, placement of the catheter, and any dose of PVSRIPO will be evaluable for both toxicity and efficacy of agent.

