15.1 Analysis Sets

All patients who receive PVSRIPO treatment will be included in all safety and efficacy analyses.

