15.5 Secondary Objective

The secondary objective is the estimation of overall survival (OS), which will be calculated as the time between PVSRIPO infusion and death, or last follow-up if the patient remains alive. The Kaplan-Meier estimator will be used to describe the survival of patients treated with PVSRIPO. Median OS will be estimated, as well as 6-, 12-, and 24-month OS. Analyses will be stratified by histologic grade.

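### Medulloblastoma and ATRT are eligible and enter every efficacy analysis, but the objectives name only malignant glioma, so the survival estimate and a grade stratum may include tumors outside the stated target

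*Combined protocol and SAP*

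**What the plan says.** **Eligibility.** Inclusion criterion 1 in Section 11.1 lists Grade III gliomas and then "WHO Grade IV malignant glioma, medulloblastoma, or atypical teratoid/rhabdoid tumor (ATRT) based on imaging studies". Criterion 1a adds: "The prior histopathology must be consistent with a World Health Organization (WHO) Grade III or IV malignant tumor". It says tumor, not glioma. The widening is deliberate: after describing CD155 expression in medulloblastoma, ATRT and embryonal tumors, Section 7.3 says "so these histologies will be included here as well".

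**Objectives.** Table 1 in Section 8 gives the secondary objective as "Estimate Overall Survival (OS) in children with recurrent WHO Grade III and IV malignant glioma treated with a single dose of PVSRIPO", and Section 5.1 uses the same population. The primary objective in Sections 5.1 and 15.4 is also limited to malignant glioma. Both sections spell out Grade IV as glioblastoma and gliosarcoma.

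**Analysis.** Section 15.1: "All patients who receive PVSRIPO treatment will be included in all safety and efficacy analyses". Section 9.4 says that any patient who has surgery, a catheter and any dose "will be evaluable for both toxicity and efficacy of agent". Section 15.5 uses Kaplan-Meier for treated patients, with median, 6-, 12- and 24-month OS, and adds: "Analyses will be stratified by histologic grade". Section 5.5 agrees. No section defines a glioma-only set, a histology stratum or a sensitivity analysis by histology.

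**The concern.** The population that may enroll and be analyzed is wider than the population the objectives describe. A treated medulloblastoma or ATRT patient would count in an OS estimate whose stated target is "children with recurrent WHO grade III and IV malignant glioma treated with a single dose of PVSRIPO". Stratifying by grade does not separate such a patient, because criterion 1a means that every eligible tumor is Grade III or IV.

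The case is not remote by design. Section 7.3 justifies the lower age limit partly by the younger peak incidence of embryonal tumors, and it counts medulloblastoma among the predominant tumors at ages 4 to 11.

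What is at stake is interpretation. With at most 12 patients, the meaning of the two-year figure depends on which histologies happen to be enrolled. The study is unblinded and has no control group. Without a prespecified rule, whether to report OS with or without the non-gliomas would be decided once outcomes are known.

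**Working it through.** **1. The plan's own figures.** The documents give no expected survival rate, no expected number of non-glioma patients and no stratum sizes. Section 15.9 states only a maximum of 12 patients. The one computed operating characteristic is Table 5, on suspension for acute toxicity. Applying the Table 4 thresholds after each patient with exact binomial probabilities reproduces its suspension probabilities to within 0.005 (for example 0.408 against the printed 0.411 at a true rate of 0.20). This point changes nothing in Table 5.

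**2. The sections side by side.**

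| Question | Section | Answer |
|---|---|---|
| Who may enter? | 11.1, 7.3 | Grade III/IV glioma, medulloblastoma, ATRT |
| Who is analyzed for efficacy? | 9.4, 15.1 | Everyone treated |
| Whom do the objectives name? | 5.1, Table 1, 15.4 | Grade III/IV malignant glioma |
| How is OS split? | 5.5, 15.5 | By grade only |

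The first two rows agree with each other. The third is narrower, and the fourth provides no way to recover it.

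**3. Size of a possible shift (illustration).** With k non-glioma patients among N and no censoring before 24 months,

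pooled OS = [(N − k) × S_glioma + k × S_other] / N.

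Assumed inputs, none from the documents: S_glioma = 10%; S_other from 0% to 50%; a Grade IV stratum of 8.

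- N = 8, k = 1: (7 × 0.10 + 0) / 8 = 8.8%, up to (0.70 + 0.50) / 8 = 15.0%.
- N = 8, k = 3: (5 × 0.10 + 0) / 8 = 6.3%, up to (0.50 + 3 × 0.50) / 8 = 25.0%.
- N = 12, k = 1: (11 × 0.10 + 0) / 12 = 9.2%, up to (1.10 + 0.50) / 12 = 13.3%.
- N = 12, k = 3: (9 × 0.10 + 0) / 12 = 7.5%, up to (0.90 + 1.50) / 12 = 20.0%.
- k = 0: no shift.

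The shift can go either way, depending on whether S_other lies below or above S_glioma.

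**4. Against sampling error.** The exact 95% interval is 0.2% to 38.5% for 1 of 12 alive, and 0.3% to 52.7% for 1 of 8. Every shifted value above lies inside the corresponding interval.

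**The case against.** The strongest reply is that the analysis text is coherent and only the objective wording lags. The histologies were added on purpose, every dosed patient is evaluable, and Section 15.5 speaks of the survival of treated patients. On this view, widening the objectives settles the matter. That stands as a legitimate way to reconcile the text, but text must change either way, and an all-treated figure alone would still not answer the glioma question now posed.

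OS is also secondary and descriptive. It has no test, power calculation or decision rule, and the monitoring rules in Section 15.4.1 rest on toxicity and inflammatory reactions. This limits the consequence.

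A glioma-only estimate would not be homogeneous either, since the protocol's own Grade III list runs from anaplastic astrocytoma to ependymoma. That is true. The aim of the fix is agreement with the stated target, not homogeneity.

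Three stronger readings are tempting, and the documents do not support them:

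- *Mixing is certain.* It needs at least one such patient to be treated. Criterion 1 requires a supratentorial tumor, and exclusion criterion 10 removes cerebellar lesions and leptomeningeal disease among others. These make it less likely but do not rule it out.
- *The Grade IV stratum is the one affected.* No section grades medulloblastoma or ATRT. Grade IV is an inference from the order of words in criterion 1; criterion 1a guarantees only Grade III or IV.
- *OS will be inflated, or a comparison with historical glioma data is spoiled.* No survival rates are given from which to derive a direction, and no historical comparison is planned.

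**Conclusion.** The mismatch between the objectives and the eligible and analyzed population is established by the text. Its effect on the OS estimate is conditional: if any medulloblastoma or ATRT patient is treated, the overall estimate and one grade stratum will contain a tumor outside the stated target. The primary safety objective has the same wording gap, though analyzing all treated patients for safety is sound.

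Neither direction nor size can be derived from the documents. The range of 6.3% to 25.0% for 3 of 8 rests wholly on the assumed rates, split and stratum size, and it lies within sampling error. This is therefore a question of which population is being estimated, and more precision would not cure it. It should be corrected because the remedy is cheap and is best fixed before outcomes are known, but it does not threaten the study's main safety conclusions.

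**What to change.** 1. **Safety.** Keep all treated patients in the safety analysis. Widen the primary objective in Section 5.1, Table 1 and Section 15.4 to the eligible histologies.
2. **Survival.** In Sections 9.4, 15.1 and 15.5, prespecify that the OS estimate answering the glioma objective, overall and by grade, uses only the glioma histologies listed in Section 5.1. List medulloblastoma and ATRT patients individually, with survival time and status. Carry the same wording into Section 5.5.
3. **Alternative.** If the sponsor prefers to widen the OS objective to all eligible histologies, report the glioma-only estimate alongside the all-treated one.
4. **Related wording.** Section 7.3 says embryonal tumors in general are included, whereas criterion 1 names only medulloblastoma and ATRT. Reconcile the two.

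**Cost.** These are text changes. Histology is already confirmed at entry and at biopsy, so no new data are needed. The price is a smaller denominator for glioma OS. If 3 of 12 patients were non-glioma, it would fall to 9, and the exact 95% interval for one survivor would widen from 0.2%–38.5% (1 of 12) to 0.3%–48.2% (1 of 9). With no such patient there is no loss.

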11.2 Exclusion Criteria

- 1. Pregnant or breast-feeding. Female patients of child-bearing potential or female sexual partners (who are of child-bearing potential) of male patients must use at least one of the following methods of medically acceptable contraceptives: approved hormonal contraceptives (such as birth control pills, patches, implants or infusions), an intrauterine device (IUD), or a barrier method of contraception (such as a condom or diaphragm) used with spermicide. Because all patients are required to have a boost immunization of trivalent inactivated IPOL™, there should be no risk of transmission of a mother to her fetus after receiving intracranial PVSRIPO. As such, patients who become pregnant after receiving PVSRIPO will continue to be monitored in the same manner, i.e. per protocol, unless the assessment is contra-indicated during pregnancy. Partners who become pregnant will sign a Pregnant Partner Information Form and information regarding the pregnancy and its outcome may be collected.
- 2. Patients with an impending, life-threatening cerebral herniation syndrome, based on the assessment of the study neurosurgeon.
- 3. Patients with an active infection requiring intravenous treatment or having an unexplained febrile illness ($T_{max} > 99.5^{\circ}\text{F}$).

4. Patients with known immunosuppressive disease or known human immunodeficiency virus infection.
5. Patients with unstable or severe intercurrent medical conditions such as severe heart (New York Heart Association Class 3 or 4) or lung (FEV₁ < 50%) disease, uncontrolled diabetes mellitus.
6. Patients with allergy to human serum albumin.
7. Patients with a known severe allergy (anaphylaxis) to gadolinium. Patients with mild allergies (e.g., rash only) are eligible and may be pretreated per institutional guidelines prior to injection of the contrast agent.
8. Patients with a previous history of neurological complications due to PV infection..
9. Patients who have not recovered from the toxic effects of prior chemo- and/or radiation therapy. Guidelines for this recovery period are dependent upon the specific therapeutic agent being used:
 - a. Patients who are less than 12 weeks from radiation therapy, unless progressive disease outside of the radiation field or 2 consecutive scans with disease progression or histopathologic confirmation of recurrent tumor.
 - b. Patients who have received chemotherapy or bevacizumab ≤ 4 weeks [except for nitrosourea (6 weeks) or metronomic dosed chemotherapy such as daily etoposide or cyclophosphamide (1 week)] prior to starting the study drug unless patients have recovered from side effects of such therapy.
 - c. Patients who have received immunotherapy ≤ 4 weeks prior to starting the study drug unless patients have recovered from side effects of such therapy.
10. Patients with neoplastic lesions in the brainstem, cerebellum, spinal cord, intraventricular tumors, pituitary tumors, leptomeningeal disease, or other locations at the discretion of the treating neurosurgeon.
11. Patients with a diagnosis of agammaglobulinemia, that is:
 - a. Undetectable anti-tetanus toxoid IgG
 - b. Known history of agammaglobulinemia
12. Patients who are on dexamethasone receiving > 4 mg/day in the two weeks prior to admission for intra-cerebral delivery of PVSRIPO or who demonstrate worsening steroid myopathy.
13. Patients with prior, unrelated malignancy requiring current active treatment with the exception of cervical carcinoma *in situ* and adequately treated basal cell or squamous cell carcinoma of the skin.

